## SYNOPSIS

Protocol Title:	A Phase 3, Multicenter, Randomized, Controlled, Double-Masked Clinical Trial to Evaluate the Efficacy and Safety of OC-01 (varenicline) Nasal Spray on Signs and Symptoms of Dry Eye Disease (The ONSET-2 Study)
Protocol Number:	OPP-101
Investigational Product:	OC-01 (varenicline) Nasal Spray: 
 
• 0.6 mg/mL
 
• 1.2 mg/mL
 

Study Objective:	The objective of this study is to evaluate the safety and effectiveness of OC-01 (varenicline) Nasal Spray as compared to placebo on signs and symptoms of dry eye disease (DED)
Overall Study Design	
Structure:	A Phase 3, multicenter, randomized, controlled, double- masked study
Duration:	Four (4) study visits over approximately 28 days during the treatment period with three (3) additional long-term follow-up visits at 6 weeks, 6 months, and 12 months.
Control:	Placebo (OC-01 Vehicle Nasal Spray)
Dosing Regimen:	Intranasal delivery of OC-01 twice daily (BID) for 28 days of one of the following dose groups: 
 
• 0.6 mg/mL
 
• 1.2 mg/mL
 
• Placebo (vehicle)
 

Summary of Visit Schedule:	
Visit 1- Screening and randomization (Day 1)  Visit 2- Dosing Compliance Assessment (Week 1)  Visit 3- Schirmer's Score Assessment (Week 2)  Visit 4- Primary and Secondary Endpoint Assessment
 
 
• Symptom Assessment (EDS) in Controlled Adverse Environment (CAE) Chamber (Week 4)
 
• Schirmer's Score Assessment; Eye Dryness Score (EDS) Assessment (Week 4)
 
 
Visit 5 – Safety Assessment (Week 6)  Visit 6- Safety Assessment (Month 6)  Visit 7- Safety Assessment (Month 12)

OC-01 (varenicline) Nasal Spray  
 Clinical Trial Protocol # OPP-101  
 Amendment #1

Sponsor: Oyster Point Pharma, Inc.  

Measures Taken to Reduce Bias:	This is a randomized, double-masked study
Study Population Characteristics	
Number of Subjects:	Approximately 750 (250 per treatment arm)
Condition/Disease:	Dry Eye Disease
Inclusion Criteria:	
Subjects must:
 
 
1. 
 
2. Have used and/or desired to use an artificial tear substitute for dry eye symptoms within 6 months prior to Visit 1
 
3. 
 
 

OC-01 (varenicline) Nasal Spray  
Clinical Trial Protocol # OPP-101  
Amendment #1

Sponsor: Oyster Point Pharma, Inc.

[REDACTED]

	[REDACTED]
--	------------

 [REDACTED]

OC-01 (varenicline) Nasal Spray  
Clinical Trial Protocol # OPP-101  
Amendment #1

Sponsor: Oyster Point Pharma, Inc.  
[REDACTED]

Exclusion Criteria:
	
Subjects must not:
 
[REDACTED]
 
[REDACTED]
 
[REDACTED]
 
[REDACTED]
 
[REDACTED]
 
[REDACTED]
 
[REDACTED]
 
6. Have had any intraocular surgery (such as cataract surgery) or extraocular surgery in either eye within three months or refractive surgery (e.g. laser-assisted in-situ keratomileusis, laser epithelial keratomileusis, photorefractive keratectomy or corneal implant) within twelve months of Visit 1
 
[REDACTED]
 
[REDACTED]
 
[REDACTED]
 
[REDACTED]
 
[REDACTED]
 
[REDACTED]
 
12. Have a history or presence of any ocular disorder or condition in either eye that would, in the opinion of the Investigator, likely interfere with the interpretation of the study results or participant safety such as significant corneal or conjunctival scarring; pterygium or nodular pinguecula; current ocular infection, conjunctivitis, or inflammation not associated with dry eye; anterior (epithelial) basement membrane corneal dystrophy or other clinically significant corneal dystrophy or degeneration; ocular herpetic infection; evidence of keratoconus; etc. Blepharitis not requiring treatment and mild meibomian gland disease that are typically associated with DED are allowed.
 
[REDACTED]
 
[REDACTED]
 
14. Have a systemic condition or disease not stabilized or judged by

-----------------------------------	--

OC-01 (varenicline) Nasal Spray  
Clinical Trial Protocol # OPP-101  
Amendment #1

Sponsor: Oyster Point Pharma, Inc.  
[REDACTED]

	
the Investigator to be incompatible with participation in the study or with the lengthier assessments required by the study (e.g., current systemic infection, uncontrolled autoimmune disease, uncontrolled immunodeficiency disease, history of myocardial infarction or heart disease, etc.)
 
15. Have a known hypersensitivity to any of the procedural agents or study drug components
 
[REDACTED]
 
[REDACTED]
 
[REDACTED]
 
[REDACTED]
 
[REDACTED]
 
[REDACTED]
 
[REDACTED]
 
18. Have any condition or history that, in the opinion of the investigator, may interfere with study compliance, outcome measures, safety parameters, and/or the general medical condition of the subject
 
[REDACTED]
 
[REDACTED]
 
[REDACTED]

--	---

OC-01 (varenicline) Nasal Spray  
 Clinical Trial Protocol # OPP-101  
 Amendment #1

Sponsor: Oyster Point Pharma, Inc.

Study Formulations:	
Subjects will be randomized 1:1:1 to be treated with OC-01 (varenicline) Nasal Spray delivered as a 50 microliter (<math>\mu\text{L}</math>) spray in each nostril at the following formulations:
 
 
• 0.6 mg/mL
 
• 1.2 mg/mL
 
• Placebo (vehicle)
 

Randomization:	
The randomization will be stratified by three factors:
 
 
• Pre-procedure (Baseline) anesthetized Schirmer's score (<math>\leq 5</math>, <math>> 5</math>) measured the screening/randomization visit
 
• Pre-procedure (Baseline) EDS (<math>< 60</math>, <math>\geq 60</math>) measured at the screening/randomization visit
 
• Study site
 
 
A central randomization list will be created using block randomization. Sites will be assigned entire blocks as needed.

Evaluation Criteria	
Efficacy Measures:	
Primary Endpoint:
 
 
• Percent of subjects who achieve <math>\geq 10</math> mm improvement in Schirmer's Test Score from baseline at Visit 4 (Day 28)
 
 
Secondary Endpoints
 
 
• Mean change from Baseline in Eye Dryness Score (EDS) at 5 minutes after threshold defined treatment administration in the Controlled Adverse Environment® Chamber at Visit 4 (Day 28)
 
• Mean change from Baseline in Eye Dryness Score (EDS) at Visit 4 (Day 28) (Post STS)
 
• Mean change from Baseline in Schirmer's Test Score (STS) at Visit 4 (Day 28).
 
• Mean change from Baseline in Corneal Fluorescein Staining at Visit 4 (Day 28)
 

Safety Measures:	
 
• Adverse Event (AE) Query
 
• Intranasal Exam
 
• Slit Lamp Biomicroscopy
 

Other Efficacy Measures:	N/A

OC-01 (varenicline) Nasal Spray  
Clinical Trial Protocol # OPP-101  
Amendment #1

Sponsor: Oyster Point Pharma, Inc.

### Summary of Known and Potential Risks and Benefits to Human Subjects

The administration of OC-01 0.6 mg/mL and 1.2 mg/mL (varenicline) Nasal Spray was safe, well tolerated, and efficacious as assessed in the ONSET-1 study. The study met the primary endpoint (Schirmer's Test) for both the 0.6 mg/mL and 1.2 mg/mL dose groups. It also met the secondary symptom endpoints (EDS) for 0.6 mg/mL OC-01 (varenicline) Nasal Spray. There was not a statistically significant improvement in EDS in the normal environment at Day 28 for the 1.2 mg/mL dose, although there was a numerical benefit as compared to placebo. Because of the pre-specified hierarchical approach to multiplicity for the secondary outcomes, the EDS symptoms within the CAE® environment at Day 21 could not be formally tested; however, the data strongly suggest benefit on that outcome as well. Although the low dose of 0.12 mg/mL OC-01 (varenicline) Nasal Spray demonstrated statistical significance in Schirmer's Score in exploratory analyses, this dose did not yield statistically significant difference in the symptom endpoint in exploratory analyses as measured by EDS.

Showing statistical significance in both signs and symptoms of DED in the same study population is a goal seldom before achieved in the treatment of the disease. Importantly, after treatment with OC-01 (varenicline) Nasal Spray, improvements in EDS were seen as early as 5 minutes after administration in the CAE® in the 0.6 mg/mL and 1.2 mg/mL OC-01 (varenicline) Nasal Spray dose groups. Exploratory analyses of fluorescein corneal staining indicate a benefit in subjects treated with OC-01 (varenicline) Nasal Spray compared to those subjects treated with placebo.

OC-01 (varenicline) Nasal Spray was safe and well-tolerated at all concentrations assessed in the ONSET-1 clinical study. Most TEAEs were mild to moderate in severity, with only 1 subject reporting a severe TEAE.

The most common AE in all treatment groups was sneezing which was temporally related to the administration of the study drug and resolved within a short period of time after administration. Sneezing AEs were characterized as mild to moderate, with no severe AEs reported.

All AEs that were suspected to be related to the study drug with the exception of AEs with each of the following terms; nasal dryness, nasal congestion and throat irritation were reported to be recovered/or resolved before study completion. Eleven ocular TEAEs were reported, 7 of which were reported in the placebo group; all other AEs were classified as non-ocular. The Investigators considered 3 of the 7 ocular TEAEs (visual acuity reduced, conjunctival hemorrhage, and eyelid oedema) to be possibly related to study drug, all resolved, and none was categorized as severe. One treatment-emergent SAE (anemia) was reported and was considered to be unrelated to study drug. No treatment-related treatment-emergent SAEs were observed. No deaths occurred during the study. Visual acuity, slit-lamp biomicroscopy, intranasal examination, and pupil diameter did not indicate clinically significant changes from baseline. These data from the ONSET-1 study suggest that 28 days of BID delivery of OC-01 (varenicline) Nasal Spray is safe and efficacious in subjects with DED.

OC-01 (varenicline) Nasal Spray  
 Clinical Trial Protocol # OPP-101  
 Amendment #1  
 Table of Contents

Sponsor: Oyster Point Pharma, Inc.

Synopsis .....	3
List of Abbreviations .....	13
1 Introduction .....	14
2 Study Objectives .....	15
3 Clinical Hypotheses .....	16
4 Overall Study Design .....	16
5 Study Population .....	16
5.1 Number of Subjects .....	16
5.2 Study Population Characteristics .....	16
5.3 Inclusion Criteria .....	16
5.4 Exclusion Criteria .....	18
5.5 Withdrawal Criteria .....	19
6 Study Parameters .....	20
6.1 Efficacy Measures .....	20
6.1.1 Primary Efficacy Measure .....	20
6.1.2 Secondary Efficacy Measure .....	20
6.2 Safety Measures .....	20
6.3 Other Measures .....	20
7 Study Materials .....	20
7.1 Study Drug(s) .....	20
7.1.1 Regimens.....	20
7.1.2 Dispensation Schedule .....	21
7.1.3 General Appearance.....	21
7.2 Other Study Supplies .....	21
8 Study Methods and Procedures .....	21
8.1 Participant Entry Procedures .....	21
8.1.1 Overview.....	21
8.1.2 Informed Consent.....	21
8.1.3 Washout Intervals .....	22
8.1.4 Procedures for Final Study Entry.....	22

### LIST OF ABBREVIATIONS

AE	Adverse event
ANCOVA	Analysis of covariance
BCVA	Best corrected visual acuity
BID	Two times a day
CAE ®	Controlled adverse environment
CFR	Code of Federal Regulations
CI	Confidence interval
CRF	Case report form
eCRF	Electronic Case Report Form
EDS	Eye Dryness Score
DED	Dry eye disease
HIPAA	Health Information Portability and Accountability Act
IB	Investigator's Brochure
ICF	Informed consent form
ICH	International Conference on Harmonisation
IRB	Institutional Review Board
ITT	Intention to Treat
logMAR	Logarithm of the minimum angle of resolution
LS	Least Square
MAD	Mucosal Atomization Device
MedDRA	Medical Dictionary for Regulatory Activities
MI	Multiple imputation
mg	Milligram
mL	Milliliter
µL	microliter
mm	Millimeter
nAChR	Nicotinic acetylcholine receptor
OSDI ®	Ocular Surface Disease Index ®
PP	Per Protocol
SAE	Serious adverse event
SAP	Statistical Analysis Plan
STS	Schirmer's Test Score
TEAE	Treatment-emergent adverse event
US	United States

OC-01 (varenicline) Nasal Spray  
Clinical Trial Protocol # OPP-101  
Amendment #1

Sponsor: Oyster Point Pharma, Inc.

## 1 INTRODUCTION

Dry eye disease (DED) is a multifactorial, age-related disorder of the ocular surface resulting

[Redacted text block]

[Redacted text block]

[figure not shown]
[Redacted text block]

[Redacted text block]

[Redacted text block]

OC-01 (varenicline) Nasal Spray  
Clinical Trial Protocol # OPP-101  
Amendment #1

Sponsor: Oyster Point Pharma, Inc.

**2 STUDY OBJECTIVES**

The objective of this study is to evaluate the safety and effectiveness of OC-01 (varenicline) Nasal Spray as compared to placebo on signs and symptoms of dry eye disease (DED).

OC-01 (varenicline) Nasal Spray  
Clinical Trial Protocol # OPP-101  
Amendment #1

Sponsor: Oyster Point Pharma, Inc.

**3 CLINICAL HYPOTHESES**

This study is testing the hypothesis that OC-01 (varenicline) Nasal Spray is superior to placebo in treating the signs and symptoms of DED.

**4 OVERALL STUDY DESIGN**

Protocol OPP-101 is a Phase 3, multicenter, randomized, controlled, double- masked study designed to evaluate the safety and efficacy of OC-01 (varenicline) Nasal Spray in adult participants with DED. Approximately 750 subjects at least 22 years of age with a physicians' diagnosis of dry eye disease and meeting all other study eligibility criteria will be randomized to receive an application of OC-01 (varenicline) Nasal Spray or placebo twice daily (BID) for 28 days with three additional long-term follow-up visits at 6 weeks, 6 months and 12 months.

Participants who terminate early during the application period will be asked to complete safety assessments (if the participants agree) prior to study exit. Participants who are terminated early from the study will not be replaced.

**5 STUDY POPULATION**

**5.1 Number of Subjects**

Approximately 750 participants (approximately 250 per arm) will be enrolled in approximately 25 sites in the US. Subjects will be randomized 1:1:1 to receive one of the following three dose assignments. All doses will be delivered as a 50 microliter (µL) intranasal spray in each nostril BID for a total of 28 days:

- Placebo (vehicle) [control]
- OC-01 (varenicline) Nasal Spray, 0.6 mg/mL
- OC-01 (varenicline) Nasal Spray, 1.2 mg/mL

**5.2 Study Population Characteristics**

All subjects must be at least 22 years of age, of either gender, and of any race, and must meet all inclusion criteria and none of the exclusion criteria.

**5.3 Inclusion Criteria**

**Subjects must:**

- 1.
2. Have used and/or desired to use an artificial tear substitute for dry eye symptoms within 6 months prior to Visit 1
- 3.

OC-01 (varenicline) Nasal Spray  
Clinical Trial Protocol # OPP-101  
Amendment #1

Sponsor: Oyster Point Pharma, Inc.

[REDACTED]

4. [REDACTED]

OC-01 (varenicline) Nasal Spray  
Clinical Trial Protocol # OPP-101  
Amendment #1

Sponsor: Oyster Point Pharma, Inc.

**5.4 Exclusion Criteria**

**Subjects must not:**

[REDACTED]

- 6. Have had any intraocular surgery (such as cataract surgery) or extraocular surgery in either eye within three months or refractive surgery (e.g. laser-assisted in-situ keratomileusis, laser epithelial keratomileusis, photorefractive keratectomy or corneal implant) within twelve months of Visit 1

[REDACTED]

- 12. Have a history or presence of any ocular disorder or condition in either eye that would, in the opinion of the Investigator, likely interfere with the interpretation of the study results or participant safety such as significant corneal or conjunctival scarring; pterygium or nodular pinguecula; current ocular infection, conjunctivitis, or inflammation not associated with dry eye; anterior (epithelial) basement membrane corneal dystrophy or other clinically significant corneal dystrophy or degeneration; ocular herpetic infection; evidence of keratoconus; etc. Blepharitis not requiring treatment and mild meibomian gland disease that are typically associated with DED are allowed.

- 14. Have a systemic condition or disease not stabilized or judged by the Investigator to be incompatible with participation in the study or with the lengthier assessments required by the study (e.g., current systemic infection, uncontrolled autoimmune disease, uncontrolled immunodeficiency disease, history of myocardial infarction or heart disease, etc.)

- 15. Have a known hypersensitivity to any of the procedural agents or study drug

OC-01 (varenicline) Nasal Spray  
Clinical Trial Protocol # OPP-101  
Amendment #1

Sponsor: Oyster Point Pharma, Inc.

components

- 16. [REDACTED]

18. Have any condition or history that, in the opinion of the investigator, may interfere with study compliance, outcome measures, safety parameters, and/or the general medical condition of the subject

[REDACTED]

### 5.5 Withdrawal Criteria

If at any time during the study the Investigator determines that a subject's safety has been compromised, the subject may be withdrawn from treatment, but will be followed for safety for the duration of the study, unless they refuse to attend follow-up visits. Subjects will be asked to attend Visit 4b, Visit 5, Visit 6 and Visit 7 for endpoint and safety assessments.

Subjects may withdraw consent from the study at any time.

Sponsor and/or Investigator may discontinue any subject from study treatment for non-compliance or any valid medical reason during the course of the study (see [Section 8.6.2](#)).

OC-01 (varenicline) Nasal Spray  
Clinical Trial Protocol # OPP-101  
Amendment #1

Sponsor: Oyster Point Pharma, Inc.

## 6 STUDY PARAMETERS

### 6.1 Efficacy Measures

#### 6.1.1 Primary Efficacy Measure

The following primary endpoints will be tested:

- Percent of subjects who achieve  $\geq 10$  mm improvement in Schirmer's Test Score (STS) from baseline at Visit 4 (Day 28)

#### 6.1.2 Secondary Efficacy Measure

- Mean Change from Baseline in Eye Dryness Score (EDS) at 5 minutes after threshold defined treatment administration in the Controlled Adverse Environment® Chamber at Visit 4 (Day 28)
- Mean Change from Baseline in Eye Dryness Score (EDS) at Visit 4 (Day 28) (Post STS)
- Mean Change from Baseline in Schirmer's Test Score (STS) at Visit 4 (Day 28)
- Mean Change from Baseline in Corneal Fluorescein Staining at Visit 4 (Day 28)

### 6.2 Safety Measures

- Adverse Events
- Intranasal Exam
- Slit Lamp Biomicroscopy

### 6.3 Other Measures

- Urine pregnancy test (Visit 1 and Visit 4a/ET)

## 7 STUDY MATERIALS

### 7.1 Study Drug(s)

#### 7.1.1 Regimens

The study drug will be delivered as a 50 microliter ( $\mu\text{L}$ ) intranasal spray in each nostril BID:

- OC-01 (varenicline) Nasal Spray, 0.6 mg/mL
- OC-01 (varenicline) Nasal Spray, 1.2 mg/mL
- Placebo (vehicle)

OC-01 (varenicline) Nasal Spray  
Clinical Trial Protocol # OPP-101  
Amendment #1

Sponsor: Oyster Point Pharma, Inc.

### 7.1.2 Dispensation Schedule

- At Visit 1, qualified subjects will be randomized and the first dose of study drug will be administered in office concurrent with Schirmer's test. The second daily administration will happen at home.
- At Visit 2, study drug/placebo will not be administered in office. Subject will self-administer study drug/placebo following their routine schedule.
- At Visit 3 the first daily dose of study drug will be administered in office concurrent with Schirmer's testing. The second daily administration will happen at home.
- At Visit 4a subjects will receive their first daily dose of study drug during CAE® exposure. The second daily administration will happen at home.
- At Visit 4b the first daily dose of study drug will be administered in office concurrent with Schirmer's testing.
- Between clinic visits, subjects will self-administer OC-01 (varenicline) Nasal Spray BID as a 50 µL dose in each nostril.

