### **ADMINISTRATION OF INVESTIGATIONAL DRUG/PLACEBO**

OC-01 (varenicline) Nasal Spray  
Clinical Trial Protocol # OPP-101  
Amendment #1

Sponsor: Oyster Point Pharma, Inc.

Treatment with Investigational drug/placebo will be administered upon a participant's reporting an Ocular Discomfort score  $\geq 3$  at two or more consecutive time points in at least one eye during CAE® exposure (participants with an Ocular Discomfort rating of 3 at time = 0 for an eye must report an Ocular Discomfort rating of 4 for two consecutive measurements for that eye (i.e. Threshold). Participants with an Ocular Discomfort rating of 4 at time = 0 for an eye must report an Ocular Discomfort rating of 4 for two additional consecutive measurements for that eye, not including time = 0 measurement) using the [REDACTED] Scale. Participants will resume symptom assessments (EDS and ODS) every 5 minutes starting 1 minute after the application ends.

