9.11 Treatment Exposure

Each randomized subject will receive an application of OC-01 (varenicline) Nasal Spray or placebo twice daily (BID) for 28 days. Duration of exposure to study treatment, in days, will be summarized for all randomized subjects. Summary statistics for duration of exposure will be presented by visit and treatment group.

10 Ocular Assessments

[figure not shown]
Ocular assessments will occur at baseline and post-baseline study visits. The results, grade, clinical significance, and relatedness to administration procedure and study drug, will be listed, summarized in tables, and presented in figures as appropriate.

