10.2 Eye Dryness Score (EDS)

The Eye Dryness Score (EDS) will be assessed using a Visual Analog Scale (VAS). Subjects score EDS at Screening (Visit 1), Day 7 (Visit 2), Week 2 (Visit 3), Week 4 (Visit 4; pre-CAE®), Week 4 in the CAE® chamber (Visit 4a; pre-treatment followed by post-treatment

every 5 minutes within the CAE[®] for a total of 120 minutes), Week 4 (Visit 4b), and Early Termination (if necessary). At Visit 4, EDS from multiple time points and change in EDS from pre- to post-treatment will be collected and summarized by CAE exposure period and by treatment group. Participants will be asked to rate their ocular symptoms (both eyes simultaneously).

Some subjects did not meet the criterion of receiving a study drug during CAE[®] exposure (Ocular Discomfort score ≥ 3 at two or more consecutive time points in at least one eye during CAE[®] exposure). For such subjects, the EDS collected during CAE[®] exposure will be treated as missing and the EDS prior to entering CAE[®] will be carried forward to impute the missing EDS during CAE[®] exposure.

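### Who is dosed in the CAE chamber at Visit 4a is stated inconsistently, and SAP 10.2 assigns chamber EDS by a symptom criterion that does not match the dosing trigger

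*Protocol*

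**What the plan says.** Protocol 7.1.2 (Dispensation Schedule) covers the Visit 4a day in two statements. The first is "At Visit 4a subjects will receive their first daily dose of study drug during CAE ® exposure". The second places the other daily dose at home. Neither carries a condition.

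Protocol 8.3.1, in the Visit 4a text on administration, makes the chamber dose conditional: "Treatment with Investigational drug/placebo will be administered upon a participant's reporting an Ocular Discomfort score" of at least 3, and this must hold "at two or more consecutive time points in at least one eye during CAE ® exposure (participants" with stricter requirements for an eye already rated 3 or 4 at time 0.

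The first-listed secondary endpoint (Protocol 6.1.2; SAP 6.2) is the change in EDS "at 5 minutes after threshold defined treatment administration in the Controlled Adverse Environment" chamber.

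SAP 10.2 states: "Some subjects did not meet the criterion of receiving a study drug during CAE". It gives the criterion as a rating of at least 3 on two successive readings in either eye, with no time-0 rule. For subjects who do not meet it, chamber EDS is treated as missing and the pre-CAE value "will be carried forward to impute the missing EDS during" the exposure. SAP 10.4 restates the trigger with the rule for a time-0 rating of 3, but without the rule for a rating of 4.

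**The concern.** For a subject who does not reach the threshold, 7.1.2 and 8.3.1 cannot both be followed: one places the first daily dose in the chamber and the other withholds it there. The precedence clauses (Protocol 10.5; SAP 3) rank the SAP above the protocol on planned analyses. They do not rank two protocol sections on dosing.

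The analysis has a related gap. An EDS at five minutes after treatment exists only if the subject was treated in the chamber. SAP 10.2 sorts subjects by symptom history instead, using a criterion looser than the dosing trigger. Where the two disagree, an undosed subject is not picked up by the carry-forward rule, or a dosed subject has real post-dose readings replaced. Either error enters the first-listed secondary endpoint.

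**Working it through.** **Inputs.** The dosing rules of Protocol 7.1.2 and 8.3.1; the trigger in SAP 10.4; the criterion in SAP 10.2; and, from Protocol 10.4, 250 subjects per arm, an EDS difference of 12 and an SD of 26.

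**1. The plan's own figure.** The standard error of a difference in means is 26 × √(2/250) = 2.326, and 12/2.326 = 5.16. The readable text gives no alpha for this calculation. At an assumed two-sided 0.05, power is Φ(5.16 − 1.96) = 99.9%; at 0.025 it is 99.8%. Both are consistent with the stated figure of approximately 99%.

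**2. The four texts applied to the same subjects.** Both eyes are taken to be rated alike.

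| Discomfort ratings in the chamber | Protocol 7.1.2, read literally | Protocol 8.3.1 | SAP 10.4 trigger | SAP 10.2 criterion |
|---|---|---|---|---|
| A: 1 at time 0, later 3 and 3 | dosed | dosed | dosed | met |
| B: 3 at time 0, stays at 3 | dosed | not dosed | not dosed | met |
| C: 4 at time 0, then 4, then 3 throughout | dosed | not dosed | dosed | met |
| D: never two successive ratings of 3 or more | dosed | not dosed | not dosed | not met |

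Only A is treated the same way by all four. B fails 8.3.1 because an eye rated 3 at time 0 must later give two successive 4s. C fails because the two 4s must come in addition to the time-0 reading, a rule absent from SAP 10.4.

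**3. Consequence for the endpoint.**
- With dosing under 8.3.1, B and C have no post-dose reading. They nevertheless meet the SAP 10.2 criterion, so its carry-forward rule does not reach them.
- With dosing under a literal 7.1.2, D has real post-dose readings, which SAP 10.2 sets to missing and replaces with the pre-CAE value.

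**4. Upper bound on the number affected.** Anyone who meets the 8.3.1 threshold also meets the SAP 10.2 criterion, because two successive 4s are two successive ratings of at least 3. Both kinds of disagreement therefore lie within the share f of subjects below the 8.3.1 threshold, and at most 250 × f per arm are affected. The documents do not give f. Assumed values of 5%, 10%, 20% and 40% give at most 12.5, 25, 50 and 100 per arm. The number actually misassigned would be smaller unless every such subject fell into B or C, or every one were dosed as in D.

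**5. Undosed subjects and power.** Suppose a share f contributes no difference between arms, the SD stays at 26, and the 12-unit difference carries over to the chamber endpoint. The mean difference is then 12 × (1 − f). At f = 20% it is 9.6 and power is 98.5%; at f = 40% it is 7.2 and power is 87.2% (two-sided 0.05). This loss comes from having undosed subjects at all, not from the mismatch between sections.

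**The case against.** The two protocol sections can be read together. 7.1.2 is a schedule of where each dose is taken, it says subjects rather than every subject, and it gives no dosing moment within the exposure. A site therefore needs 8.3.1 to run the visit. The endpoint name, the pre-treatment CAE procedures in 8.3.1, SAP 10.2 and SAP 10.4 all presuppose a threshold. It can also be said that the criterion in SAP 10.2 is described as the one for receiving study drug, so its parenthesis may only abbreviate the full trigger.

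Most of this stands. It makes the analysis intent fairly clear and makes dosing below threshold a possibility rather than an expectation. It does not settle the first daily dose of a subject below threshold: the self-administration statement in 7.1.2 covers the time between clinic visits, and no other legible passage addresses it. Nor does it remove the mismatch in SAP 10.2, which spells out a criterion that subjects B and C satisfy without being dosed under 8.3.1.

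Stronger readings are tempting but unsupported:
- A reader might infer that who has a five-minute post-dose EDS is left open. SAP 10.2 does provide for subjects below threshold, by carry-forward; the problem is confined to how it identifies them.
- A reader might take SAP 9.11 ("Each randomized subject will receive an application of OC-01 (varenicline) Nasal Spray or placebo twice daily (BID) for 28 days") as counting every subject as fully dosed. That section states the planned regimen and summarises exposure in days, so it does not contradict an omitted chamber dose.
- A reader might expect the primary endpoint to be affected. At most one of 28 × 2 = 56 planned dosing times differs (1.8%). Visit 4b is at least three days later, and its Schirmer's test is concurrent with a new in-office dose. The documents show no effect.

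**Conclusion.** The point holds in limited form. Protocol 7.1.2 omits the condition in 8.3.1, and the first daily dose of a subject below threshold is not addressed in the legible text. SAP 10.2 assigns chamber EDS by a criterion that can disagree with actual dosing in both directions.

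The size is unknown. The affected number is bounded by the share below the 8.3.1 threshold, which the documents do not give; the 5% to 40% range is an assumption. The stated EDS power reproduces, and the illustrative power loss should not be attributed to this inconsistency. Site-to-site variation in chamber dosing is possible but not shown.

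Two limits apply. Redacted SAP text on missing data and on the secondary analyses may contain further handling. The Appendix 1 schedule is too broken in the available text to be used as evidence either way.

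**What to change.** 1. Reconcile Protocol 7.1.2 and 8.3.1 with SAP 10.2 and 10.4, so that one rule states who is dosed in the chamber, including the time-0 cases, and what applies to the first daily dose of a subject who does not reach the threshold. The clinical choice is the sponsor's.
2. In SAP 10.2, replace the symptom criterion with recorded chamber dosing (yes/no and time) to decide whose post-dose chamber EDS is used and whose pre-CAE EDS is carried forward.
3. Report by arm the numbers dosed and not dosed in the chamber.

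The cost is a clarifying sentence in the protocol, a short SAP revision, a little extra programming, and an eCRF field if chamber dosing and its time are not already captured. No additional visits or subjects are needed.
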